## **11. Human Subjects Protection**

### **a. Subject selection**

Accrual will be equitable among the participants eligible for this study.

We are excluding people over 50 years of age because older adults have elevated pain thresholds for brief pain stimuli [27] and there is no evidence that their discriminative functions are unchanged.

### **b. Justification for exclusion of children**

The current study constitutes initial research into the sensory mechanisms underlying deep pressure touch and involves an ischemic compression block which is a procedure likely to not be well tolerated by children, with no particular benefit to them. Results are very likely to generalize to children since the role of sensory afferents is consistent across the lifetime. To confirm this a separate, age-specific study in children would be warranted and preferable and children will not be included in the current study.

### **c. Justification for exclusion of other vulnerable subjects**

Participants who do not speak English will not be enrolled because clear, rapid and direct communication is needed with all members of the study team, due to the rapid progression of the nerve block. Further, VAS rating scales we will use have not been validated in languages other than English.

Individuals without consent capacity will be excluded because the research question can be answered by enrolling only adults who can consent, and participation does not offer the potential for important clinical benefit. Therefore, the risk outweighs the benefit in this population.

Pregnant women and lactating women are excluded because pregnancy and lactation significantly alter a women's hormonal profile and hormones affect touch processing [25, 26], and because nerve blocks may cause vasovagal responses that could affect a developing fetus.

We are excluding individuals who work at NIH and are subordinates, relatives, or co-workers of the investigators, or NCCIH DIR employees. Other NIH staff may participate.

**d. Justification for sensitive procedures**

N/A

**e. Safeguards for vulnerable populations and sensitive procedures**

Pregnant women will be excluded from participation due to the unknown risks of performing a nerve block and altering blood pressure on the developing fetus. A pregnancy test will be conducted to protect against the inclusion of a pregnant woman. While NCCIH employees are excluded from participation, NIH employees and staff may also be considered vulnerable. Protections for employees and staff participating in this study include 1) assuring that the participation or refusal to participate will have no effect, either beneficial or adverse, on the subject's employment or position at the NIH, 2) giving employees and staff who are interested in participating the "NIH Information Sheet on Employee Research Participation" prior to obtaining consent, and 3) assuring that there will be no direct solicitation of employees or staff. This study collects sensitive information on drug use and alcohol use and specific medical diagnoses. The PI will train study staff regarding obtaining and handling potentially sensitive and private information about co-workers through staff discussions and written branch/section procedures. Prior to

enrollment, potential participants will be informed that this sensitive information will be in their NIH medical record.

## **12. Anticipated Benefit**

The study does not offer direct benefit to participants but is likely to yield generalizable knowledge about the perception of deep pressure, with potential implications for chronic pain.

## **14. Consent Documents and Process**

### **a. Consent procedures**

Informed consent for this study will be obtained in-person at the initial visit or during a separate visit prior to the study session, after the initial inclusion criteria have been met via the telephone interview, physical exam (conducted under protocol 16-AT-0077), and drug and pregnancy tests (conducted under protocol 16-AT-0077), but prior to any experimental procedure. The participants will have an opportunity to carefully review the consent and ask questions regarding this study prior to signing, and they will be informed that they may withdraw from the study at any time without prejudice to themselves. The consent procedures will be conducted in a private room by a qualified study investigator. All participants will receive a verbal explanation in terms suited to their comprehension of the purposes, procedures and potential risks of the study and of their rights as research participants. Participants will have the opportunity to carefully review the written consent form and ask questions regarding this study prior to signing. NIH employees will not be consented by a coworker.

### **b. Consent documents**

The consent form contains all required elements. The consent document is submitted with this protocol.

## **15. Data and Safety Monitoring**

### **a. Data and safety monitor**

The Principal Investigator will be responsible for monitoring data and safety.

### **b. Data and safety monitoring plan**

The Principal Investigator is responsible for maintaining adequate clinical records documenting the medical history, condition and test results for each study participant throughout the study. Source documentation may consist of written or electronic records and supporting data maintained by the PI and/or the institution. The medical records for each participant shall document that informed consent was obtained prior to participation in the study.

[name] will review progress of the study annually. Adverse events data will be reviewed as they arise to ascertain whether or not there are safety concerns with study procedures.

### **c. Criteria for stopping the study or suspending enrollment or procedures**

If there is any Serious Adverse Event (SAE) related to the research, the entire study will halt until the plan to address the SAE has been developed by the investigator, clinical director, and the IRB and SAE has resolved.,

## **16. Quality Assurance (QA)**

### **a. Quality assurance monitor**

The Principal Investigator is responsible for monitoring the quality assurance of this protocol.

### **b. Quality assurance plan**

At least annually, the PI will review all regulatory and patient information with the study team to ensure data and study integrity are maintained. Data collected on prepared questionnaire forms will be entered into a database against the original source and checked by someone other than the initial person entering data. In addition, this protocol will undergo audits by the QA audit committee as outlined in the NINDS QA SOP. This study is classified as “minimal risk” and thus will undergo random audits. The purpose of

the QA audit is to assess compliance with applicable regulatory requirements and good clinical practice guidelines, as well as to provide recommendations for improving the management of clinical research data.

## **17. Reporting of Unanticipated Problems, Adverse Events and Protocol Deviations**

Reportable events for this protocol will be tracked and reported in compliance with policy 801.

## **18. Alternatives to Participation**

Subjects do not receive any treatment in this study or forego any treatment in order to participate in this study. The alternative, therefore, is not to participate.

## **19. Privacy**

All research activities will be conducted in as private a setting as possible.

## **20. Confidentiality**

### **a. For research data and investigator medical records**

We will actively protect confidentiality of the subjects and the data at each step. All medical records and subject data will be kept confidential and will only be reviewed by the participating investigators. Data will be de-identified and stored using codes that we assign. De-identified data will be kept in encrypted password-protected NCCIH computers in rooms that are locked when not occupied. Hard copy records/data will be kept in locked cabinets in rooms that are locked when not occupied. Only study investigators will have access to the data.

Research staff will be trained by the PI to respect the privacy and confidentiality of NIH employees and staff, especially with regard to sensitive, private information. All data will be de-identified and personnel will not view data alongside identifying information, which will reduce the possibility that lab personnel would be able to associate sensitive information with individuals. The lab will discuss professionalism and confidentiality, and if lab personnel are acquainted with any potential participants, a different investigator will interact with that participant.

**b. For stored samples**

Samples will not be stored. All samples (e.g., urine samples for pregnancy tests and drug screens) will be destroyed.

## **21. Conflict of Interest**

**a. Distribution of NIH guidelines**

NIH guidelines on conflict of interest have been distributed to all investigators.

**b. Conflict of interest**

There are no conflicts-of-interest to report for NIH investigators. Non-NIH investigators will abide by the conflict-of-interest policies of their own institutions.

**c. Role of a commercial company or sponsor**

N/A

## **22. Technology Transfer**

No technology transfer agreement is required for this protocol per communication with a local technology transfer office. Agreements will be put in place if they become necessary.

## **23. Research and Travel Compensation**

Subjects will be compensated for time and research-related inconveniences (see table below) on an hourly basis. If a session cannot be completed due to unforeseen circumstances (e.g., technical issues), payment will be prorated and testing will continue in a rescheduled session. NIH employees and staff who participate during work hours

must have permission from their supervisor. NIH employees must either participate outside of work hours or take leave in order to receive compensation. Payment will be made at the completion of each session. No compensation will be made for travel. No escort fees will be provided. The Table below provides the compensation matrix that will be used for research compensation:

Study session (sensory testing with nerve block)	\$150 for clinical screening, sensory testing, and nerve block, up to 2 hours.
Overtime (Session lasts more than 2 hours due to delays with urine tests or other delays caused by staff or equipment)	\$50 per hour up to 2 additional hours.
Maximum total compensation	\$250

## 25. Attachments/Appendices

**Attachment 1:** Eligibility Checklist and Pre-Screening Telephone Interview, Pre-Session Screening, MINI

**Protocol T-AT-0345 Telephone Pre-screening**

Date of Interview: \_\_\_\_\_ Interviewed By: \_\_\_\_\_

---

Hello, this is (INTERVIEWER) calling from NCCIH. Is this \_\_\_\_\_? Do you have a few minutes to talk about a new study we have on the role of different sensory fibers in touch perception? I'd like to give you a brief description of the study, then you can ask any questions you may have, and then I'll have some questions for you.

In this study, we are interested in the role of different sensory fibers in perceiving types of touch sensations. If you are eligible and choose to participate, you will be scheduled for a single test session. This session would last approximately 2 hours. During the session you would have a brief medical exam and provide a urine sample for a drug test (and pregnancy test). Then, you would be seated in an exam room and complete some sensory testing such as detecting or rating brushing, vibration, warm sensation, cool sensation, movement, pinprick (that does not pierce the skin), or pressure on your arm or hand. Next, we would take your blood pressure and inflated a blood pressure cuff to approximately 100mmHg above your systolic BP. This causes blood flow to be cut off to your arm and will cause you to slowly lose different sensations over the course of the testing period. The sensations will return to normal after the blood pressure cuff is removed at the end of the session. While it is inflated, we will do sensory testing almost continuously to track your sensations over time as different nerve fibers become affected. The nerve block will be removed most likely by 40 minutes, or by 1 hour at the very most. After your sensation has returned to normal you will be free to leave. You will be asked to wear short sleeves or change into scrubs for each session in order to access the full arm.

There is no pain testing in this study except for the pinprick, which is a bit like a mechanical pencil- it does not penetrate the skin. However, having the blood pressure cuff inflated to cut off blood flow can cause pain or discomfort, as well as emotions of disgust in response to the limb turning pale or losing sensation. We will try our best to keep you comfortable and keep your limb covered so you are not looking at it. You may choose to end the testing early if it is not tolerable. During the sensory testing, you will experience light touch with a soft brush, a hand massager, vibration, pinprick, pressure with an inflatable arm compression sleeve, warm and cool pain sensations using a thermode, and gentle movement of your fingers.

There are no risks of our sensory testing. The risks of the nerve block (blood pressure cuff block) are mostly pain or discomfort, or the emotional response to feeling the temporary loss of sensation. However, an uncommon side effect is a vasovagal response like vomiting or fainting. If you have history of a seizure it could induce a seizure, so we would exclude you. Finally, we would exclude you if you have a history of blood clots or circulatory problems in yourself or your family, due to a rare risk of dislodging blood clots or damaging nerves.

Your urine will be tested for illegal drugs before each study session. If your drug test is positive, you will not be included in the present study. The results of the drug testing will be noted in your NIH medical record. If you do not want this information in your medical record, you should not participate in this study. In addition to this drug screening, participants who are able to become pregnant will have a pregnancy test. If positive, you will not be able to participate because it is unknown if the nerve block has any negative effects for a developing fetus.

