thermode (Medoc Pathway System; Medoc Ltd., Advanced Medical System, Israel). The Medoc thermode is used in accord with its FDA approved indication of human pain reception and transmission of sensory pathways. Warm threshold will start at approximately 32 °C and increase until the participant responds with a button press, eventually stopping at 50 °C. Cool threshold will similarly start at approximately 32 °C and decrease until the participants indicates perception of the cool, or to 0 °C. These threshold procedures are standard thermal testing procedures and have been used in our lab and elsewhere, including in currently approved NIH protocols [18].

Pinprick perception (A-delta): A pinprick (superficial; does not break skin) will be administered each test cycle and reaction time will be collected by a button press (or similar response).

Proprioception (A-alpha and A-beta): The experimenter and/or participant will move one finger up or down and the participant will indicate which direction the finger was moved in.

Pressure (unknown sensory afferent type): A quick pulse of pressure will be administered via a pressure algometric device. The participants indicate if they detected a pressure change and/or rate the intensity of the sensation from 0-10.

NRS ratings of current ongoing pain and discomfort (0-10) will be collected. 0 = no pain/no discomfort and 10 = intolerable pain or discomfort.

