### **Risks and discomforts associated with heat and cool stimuli**

The nature of the study requires the application of warm and cool stimuli that can become painfully hot or cold if not perceived at typical thresholds. However, these stimuli have been used in previous studies, have proven to be easily tolerated, and do not cause permanent tissue damage. Slight reddening or darkening of the skin may occur. This is transient and disappears after termination of the testing. Heat pain stimulation has been used extensively without any long-term adverse effects [17, 18, 24].

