### **Risks and discomforts associated with vibration, pinprick, and compression stimuli**

There are no known risks of the vibration or pinprick stimuli other than possible minor discomfort. Pressure stimuli may be uncomfortable to some participants, but the pressure will be lower than a standard blood pressure cuff and familiar to all participants. Repeated inflation could dislodge any active blood clots in the participant's arm, so all participants will be checked during medical screening to ensure they do not have any clinical signs of clots present.

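### The telephone script tells candidates that sensory testing has no risks and no pain testing beyond pinprick, which Section 7 and the script's own list of stimuli contradict

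*Combined protocol and SAP*

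**What the plan says.** **Telephone script (Attachment 1, Protocol T-AT-0345 Telephone Pre-screening).** The candidate is told: "There is no pain testing in this study except for the pinprick". Later in that paragraph the list of stimuli includes "pressure with an inflatable arm compression sleeve, warm and cool pain sensations using a thermode". The next paragraph opens with "There are no risks of our sensory testing" and then turns to the nerve block, which is where clot dislodgement is mentioned. Shortly afterwards the interviewer asks whether the candidate is still interested.

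**Section 4.d, Details of Sensory testing paradigm.** Both thermal ramps start at about 32 °C. The warm ramp will "increase until the participant responds with a button press, eventually stopping at 50 °C". The cool ramp will "decrease until the participants indicates perception of the cool, or to 0 °C". The monitoring pressure pulse is given by a device described only as algometric. Deep pressure, the outcome stimulus, is given by a hand massager.

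**Section 7, heat and cool stimuli.** The study uses "warm and cool stimuli that can become painfully hot or cold if not perceived at typical thresholds". The skin may briefly redden or darken. The section adds that these stimuli are well tolerated and leave no permanent damage.

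**Section 7, vibration, pinprick and compression stimuli.** Vibration and pinprick may cause minor discomfort, and pressure may be uncomfortable for some. The reassurance on pressure is that "the pressure will be lower than a standard blood pressure cuff and familiar to all participants". Repeated inflation is said to be capable of dislodging an active clot, and participants are checked for clinical signs of clots at medical screening.

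**The concern.** A statement that a set of procedures carries no risk is either true or false, and the protocol's own risk section names risks for the procedures in question. The script is read to every candidate who reaches telephone pre-screening and leads directly into a question about continued interest. A candidate who would decline because of painful heat or cold, or because of the clot concern with compression, has been told that sensory testing raises nothing to consider.

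The thermal element matters most because of how the study works. The participant's response is what ends a ramp short of its limit, and the block is applied in order to take sensation away. The exposure that the script leaves out is thus one that the methods make foreseeable.

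**Working it through.** No formula applies. The check sets the passages side by side.

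**1. The no-risk sentence against Section 7**

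| Stimulus | Telephone script | Section 7 |
|---|---|---|
| Thermal (thermode) | No risks | Can become painful; brief reddening or darkening of the skin |
| Pressure / compression | No risks | May be uncomfortable; repeated inflation could dislodge an active clot |
| Vibration | No risks | Possible minor discomfort only |
| Pinprick | No risks, though called pain testing | Possible minor discomfort only |

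For vibration and pinprick the gap is small. For thermal and pressure stimuli the two statements cannot both stand. The script does mention clot dislodgement, but only with the nerve block, whereas Section 7 also places it with the compression stimuli.

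**2. The pain sentence against the script itself**

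The script limits pain testing to pinprick and, in the same paragraph, names thermode pain sensations. The ramps in Section 4.d are detection thresholds, so the first statement could be read as describing intent. That reading does not rescue the second, and it does nothing for the no-risk sentence.

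**3. Are thermal stimuli beyond typical thresholds foreseeable?**

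- The available range from the starting temperature is 50 − 32 = 18 °C upward and 32 − 0 = 32 °C downward.
- With no response, Section 4.d lets the ramp continue to its limit.
- Testing is distal to the block. Section 4.d says that loss of cool and loss of light touch often coincide, and the study overview of procedures says that sensory monitoring continues after A-beta loss.
- Section 7 itself ties painful heat or cold to a failure to perceive the stimulus at typical thresholds.

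It follows that ramps past typical thresholds can be expected in some participants. It does not follow that they will reach the limits, or how often.

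**4. The monitoring pressure device (minor)**

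| Place | Description |
|---|---|
| Section 4.d | Algometric device; no inflatable test device is named |
| Section 7 | Lower pressure than a blood pressure cuff; repeated inflation |
| Telephone script | Inflatable arm compression sleeve, listed apart from the hand massager |

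The Section 7 wording fits an inflatable device. Section 4.d does not say whether the algometric device inflates. The reader cannot tell which device the Section 7 pressure statement covers. The hand massager is named consistently in Section 4.d and the script.

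**The case against.** The strongest reply is that the call is a screening contact of about 10 minutes and not the consent process. Section 14.a requires an in-person explanation of the risks, and review of a written form, before any experimental procedure. Section 8 adds instruction and practice with every sensory test. This stands as far as it goes: a reader might infer that participants enrol uninformed of thermal risk, and the documents do not support that, because the consent form is a separate document not reviewed here. A sound consent form would still not make the script accurate.

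A second reply is that Section 7 calls the thermal stimuli well tolerated and that Section 4.d describes standard procedures with stated stopping limits. That bears on how serious the omission is. It is not a reason to say that there are no risks.

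A reader might also infer that ramps on the blocked arm run to 50 °C and 0 °C by design, or might try to count them. Neither holds. The background section says that warm and cool testing is there to confirm that A-delta and C fibres still work. Section 4.d says only that monitoring may include the thermal tests, and it gives the interval of 1 to 2 minutes for the period before A-beta loss. Later monitoring has no stated frequency. A stimulus that becomes painful may itself prompt the response that ends the ramp.

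Finally, the differing descriptions of the pressure device do not prove that two devices are used. They may be loose names for one.

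**Conclusion.** The point holds for the script. The no-risk sentence contradicts Section 7 for thermal and pressure stimuli and is slightly wrong for vibration and pinprick. The pain sentence is contradicted by the script's own list of stimuli. Both should be corrected, because they are read to candidates and bear on a decision.

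The size is limited. Two sentences of participant information are wrong, and one device is described inconsistently. Nothing changes in the outcomes, the sample size of 12 completers, the power or the analysis. The conclusion rests on the text alone, except for the statement that ramps past typical thresholds are foreseeable. That is an inference from the stop-on-response rule in Section 4.d together with the wording of Section 7. The documents support no estimate of how many such ramps occur and no finding about written consent.

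**What to change.** Reconcile Attachment 1 with Sections 4.d and 7:

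- Replace the two script sentences with the Section 7 risk language, in plain terms, for thermal, pressure, vibration and pinprick stimuli, and make the script's list of stimuli agree with it.
- As a minor clarification, describe the monitoring pressure device in the same way in Section 4.d, Section 7 and the script, so that it is clear which device the Section 7 pressure statement covers.

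Any rule or limit for thermal ramps after perception is lost is for the sponsor and the responsible clinicians; none is proposed here. The cost is amended wording in the script and in the device descriptions, with no added procedure, staff or participants.
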